### Statistical Analysis Plan (SAP)

All data was coded and entered into SPSS version 27.0 (IBM Corp., Armonk, N.Y., USA) for statistical analysis. Patient participant and physical therapist participant demographic data was reported with means, ranges, and standard deviations. The primary correlational statistics was the Spearman rho to assess the various individual trust measurement scores and changes in scores over time and individual scores with the primary outcome measurements of pain, function, and global change. The individual trust measurement scores, that have not been used in physical therapy, were be analyzed for correlation to WIA-SR, which has been used in physical therapy research, with Spearman's rho. Friedman's analysis of variance looked at changes in individual trust measurement scores over time from pre-initial visit, post-initial visit, and discharge. The non-parametric analysis was used due to the ordinal nature of the outcome variables. The PT Survey of Patient Connection and Engagement was analyzed for correlation with outcomes and the individual trust measurement scales with the Spearman rho. Linear regression analysis was done with the individual trust measurement scales and outcomes variables for predictive modeling of trust and outcomes assessment.

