Once patient participants completed the informed consent process they were directed to a second PsychData link in order from them to complete a participant demographics form (Appendix B) that further verified their eligibility into the study. Inclusion criteria consisted of greater than 18 years of age, able to read, speak, and write in English, and presence of low back pain for at least 3 months. Exclusion criteria were current pregnancy or active cancer diagnosis. Patient participants were also excluded from the study if at any point during the episode of care they required different medical attention beyond physical therapy and needed to be referred out for medical reasons and had to discontinue their physical therapy prior to achieving goals. Any patient participant that did not receive at least 80% of the treatments from the initial physical therapist participant were excluded from primary data collection. Physical therapist participant inclusion criteria were having a physical therapy license to treat patients and employed at a clinic site approved for the study.

The initial *a priori* was set for a total of 64 patient participants with the primary complaint of chronic low back pain that had lasted a minimum of 3 months prior to initiating the current physical therapy episode of care. The patient were consecutively enrolled in the study at the various clinic sites. An *a priori* achieves 79% power to detect a Pearson correlation of 0.400 using a two-sided hypothesis test with a significance level of 0.05 with an included 20% dropout rate. These results are based on 1000 samples from the bivariate normal distribution under the alternative hypothesis. The number of physical therapist participants was determined by the clinic site enrollment and treating at least one patient participant during the course of the study.

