informed consent, they progressed to additional PsychData questionnaires to be filled out by the patient participant prior to their initial evaluation with their physical therapist. Information collected consisted of: baseline demographic information sheet, General Trust in Physician Scale, Trust in Physician Scale, PCAS, Wake Forest Scale, ODI, and NPRS. The online participant data collection allowed for blinding of the physical therapist throughout the study to the trust measurement scores. Patient participants received normal physical therapy evaluation and treatment as directed by the physical therapist. Upon completion of the initial visit, the patient participant completed the WAI-SR, Trust in Physician Scale, PCAS, and Wake Forest Scale through a second PyschData link. After completion of the second physical therapy visit, the participating physical therapist completed the PT Survey of Patient Connection and Engagement. Patient participants were blinded to the physical therapist's responses on this instrument. Patient participants continued to receive normal physical therapy as directed by the physical therapist working toward discontinuation of the current episode of care. The majority of the physical therapy encounters (80%) needed to have the initial physical therapist directly involved with the care of the patient participant to be eligible for data collection. If less than 80% of the visits have the direct care delivered by someone other than the initial physical therapist, that data was excluded from primary analysis. Upon discontinuation of the current episode of care or the end of 6 months of care, the patient participant completed the Trust in Physician Scale, PCAS, Wake Forrest Scale, WAI-SR, ODI, NPRS, and GROC. The participating physical therapist completed a second PT Survey of Patient Connection and Engagement at the conclusion of care. (Figure 1) Patient participants that complete all three series of forms (pre-initial visit, post-initial visit, and discontinuation episode) were eligible for a total of \$25 in Walmart gift cards to be mailed to an address of their choice.

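### Patients are tied to one therapist, but the planned associations name no therapist term; the effect depends on caseloads and ICCs that are not given, so a therapist-adjusted sensitivity analysis should stand beside the primary result

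*Combined protocol and SAP*

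**What the plan says.** The SAP states: "The primary correlational statistics was the Spearman rho to assess the various individual trust measurement scores" and their changes against pain, function and global change. Spearman rho is also used for trust against WAI-SR, and for the PT Survey against outcomes and trust. It adds: "Linear regression analysis was done with the individual trust measurement scales and outcomes variables". No therapist term, mixed model or cluster-robust error is named, although the regression covariates are not listed in full.

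Section 3.3.1 says that patients who "did not receive at least 80% of the treatments from the initial physical therapist participant were excluded from primary data collection". Section 3.3.5 adds that the majority of encounters, put at 80%, "needed to have the initial physical therapist directly involved with the care of the patient participant to be eligible for data collection". On numbers, section 3.3.1 says only: "The number of physical therapist participants was determined by the clinic site enrollment and treating at least one patient participant". That is a minimum of one patient per therapist and no maximum.

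The therapist is the object of the provider-specific trust scales and is also a rater. After the second visit "the participating physical therapist completed the PT Survey of Patient Connection and Engagement", and again when care ends. Baseline trust forms were "to be filled out by the patient participant prior to their initial evaluation with their physical therapist". Therapists received a coded ID (section 3.3.5). Therapist characteristics are to be described: "Patient participant and physical therapist participant demographic data was reported with means, ranges, and standard deviations". Caseloads and ICCs are not among the planned reports.

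**The concern.** Ordinary Spearman and least-squares tests assume independent patients. If therapists differ both in the trust they earn and in the outcomes of their patients, and each treats several patients, chance differences between a few therapists can look like a patient-level association. The usual p-value is then too small, and a trust-outcome correlation looks firmer than it is.

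This mainly concerns trust after the initial visit and at discharge (including change scores), WAI-SR, and the PT Survey. Pre-visit trust should cluster less, except perhaps in patients already treated by that therapist, which section 3.3.4 records. Friedman's test of change over time is a within-patient comparison and is not part of this point.

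The PT Survey has a further feature. A lenient or severe therapist shifts all the ratings that he or she gives. Leniency unrelated to outcome weakens rho and power, and it also makes the ratings cluster, which raises false positives when the outcome clusters too.

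**Working it through.** **Inputs from the documents (section 3.3.1).** 64 patients, 20% dropout, two-sided 0.05, correlation 0.400, power 79%, simulated from independent bivariate normal pairs.

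**The plan's own figure.** 64 × 0.80 = 51.2, so about 51 are analysed. For a Pearson test by Fisher's z: atanh(0.4) × √(51 − 3) = 0.4236 × 6.928 = 2.935, and Φ(2.935 − 1.96) = Φ(0.975) = 83.5%. A Spearman test simulated at n = 51 gives 79.6%. The stated 79%, although labelled Pearson, therefore reproduces for Spearman with 51 independent patients.

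**Assumptions.** Caseloads and ICCs are not in the documents. The layouts below all total 51 patients. The ICCs run from 0 to 0.3.

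**Approximation.** With caseloads m and no true association, the variance of the correlation is multiplied by about D = 1 + (Σm²/n − 1) × ICC₁ × ICC₂. The false-positive rate is about 2[1 − Φ(1.96/√D)].

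- One ICC zero: D = 1, rate 5.0%. Both variables must cluster.
- 25 therapists (24 with two patients, one with three), ICCs 0.3/0.3: Σm² = 96 + 9 = 105; D = 1 + (105/51 − 1) × 0.09 = 1.095; 1.96/√1.095 = 1.873; 6.1%.
- 12 unequal caseloads (14, 9, 7, 5, 4, 3, 3, 2, 1, 1, 1, 1), ICCs 0.3/0.3: Σm² = 393; D = 1 + 6.706 × 0.09 = 1.604; 1.96/√1.604 = 1.548; 12.2%.

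The formula overstates the rate when therapists are few or caseloads unequal, so simulation was used for the sizes.

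**Simulation.** Normal therapist effects, independent for the two variables; 20,000 null datasets per setting; Monte Carlo standard error about 0.2 points. False-positive rate of the nominal 5% Spearman test:

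| ICCs | 25 therapists | 13 | 12 unequal | 6 | 5 |
|---|---|---|---|---|---|
| 0.1/0.1 | 5.3% | 5.3% | 5.4% | 5.7% | 5.8% |
| 0.1/0.3 | 5.3% | 5.8% | 6.5% | 6.9% | 7.6% |
| 0.2/0.2 | 5.6% | 6.3% | 7.3% | 7.5% | 8.3% |
| 0.3/0.3 | 5.9% | 7.6% | 10.1% | 11.6% | 12.4% |

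A repeat with fresh random numbers differed by at most 0.8 points (six therapists at 0.2/0.2: 8.3%). With trust ICC 0 to 0.05 and outcome ICC 0.3, as might hold for pre-visit trust, the rate was 4.7-6.0%. Ordinary linear regression stayed within 0.5 points of Spearman. An edge case with all 64 patients analysed and six unequal therapists at 0.3/0.3 gave 14.1%.

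**PT Survey.** With within-therapist correlation 0.4, outcome ICC 0.1 and leniency at 30% of rating variance, mean rho falls from 0.36 to 0.30-0.31 and Spearman power from 75-76% to 58-61%. With no association, the same leniency and outcome ICC 0.1 or 0.3, Spearman's false-positive rate is 5.3-13.2%.

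**Therapist-adjusted test.** A random therapist intercept with Satterthwaite degrees of freedom, outcome as response, gives 4.5-6.4% on ranks and 4.8-6.9% on raw scores. For the PT Survey with the rating as response it gives 5.5-6.3%. The choice of response matters: the two directions disagree on significance in 1.4-3.2% of null datasets, and taking the smaller p-value gives 6.0-8.0%.

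**The case against.** The strongest reply is that the size rests wholly on assumed ICCs and caseloads, and much of the grid is mild. Rates above 11% in the table need five or six therapists and ICCs of 0.3 on both variables. The protocol describes multiple sites and multiple therapists, and section 3.3.1 names six states approached, so nothing points to so few. That stands, and it limits the point to a conditional one. It does not remove it: enrolment by therapist is not stated, and twelve therapists with a few busy ones already give about 10% at 0.3/0.3.

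A second reply is that a therapist-intercept model answers a different question. Rho describes the overall association, and the model leans towards the association within therapists. If some therapists earn more trust and also get better results, that is part of what the study asks. With correlation 0.2 within and 0.8 between therapists and ICCs of 0.3/0.3, mean rho is 0.33-0.36, but power falls from 64-74% (Spearman) to 43-67% (model). This stands as a reason not to replace the planned p-values.

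A reader might go further and infer that the study's true error rate is 10-12%, that the ordinary p-values are invalid, or that the regressions certainly omit the therapist. The documents support none of these. They give no ICC or caseload, and the SAP does not list the regression covariates in full.

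**Conclusion.** The point holds as a conditional weakness of moderate size. The rule in section 3.3.1 nests patients in therapists, and the SAP names nothing that allows for it. With 51 patients the nominal 5% test is:

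- about 5-6% if only one variable clusters, if both ICCs are near 0.1, or with about two patients per therapist;
- about 7-7.5% at ICCs 0.1/0.3 with few therapists or unequal caseloads;
- at 0.2/0.2, about 6% with 13 near-equal therapists and 7-8% with fewer or unequal ones;
- at 0.3/0.3, about 7.5% and 10-12% respectively.

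Which case applies cannot be told from the documents, and the planned reporting would not show it. For the PT Survey, leniency can either hide an association or, when the outcome clusters by therapist, help to produce a false one.

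**What to change.** 1. Carry the coded therapist ID on each patient record. Report patients per therapist and the ICCs beside the planned therapist demographics.
2. Keep Spearman rho and its ordinary p-value as the primary result. Pre-visit trust-outcome associations need nothing more.
3. For associations using post-visit or discharge trust (including change scores), WAI-SR or PT Survey scores, add one sensitivity analysis: a random intercept for therapist with Satterthwaite degrees of freedom, on ranks. Fix the response before the models are run, for example the outcome for trust-outcome, WAI-SR for trust-WAI-SR, and the rating for the PT Survey. The documents are written largely in the past tense, so if results have already been seen, label the choice post hoc.
4. Fit the linear regressions with the same therapist intercept.
5. State that rho describes the overall association while the model leans towards the within-therapist one. Call an association firm only if it holds in both; otherwise say that it lies mainly between therapists, where the results show that.
6. Separately, reconcile the 80% rule. One sentence in section 3.3.5 excludes data when less than 80% of visits were delivered by someone other than the initial therapist, which reverses section 3.3.1.

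The cost is a little more analysis on a therapist ID already assigned, and possibly larger p-values. The model has lower power when the association lies mainly between therapists and is only approximate with few therapists. At ICCs of 0.1/0.1 it gains nothing (5.3-6.2% against 5.3-5.8%). It cost no power without clustering (79% for both), or with a correlation of 0.4 both within and between therapists (79-81% against 75-80%).

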## Study protocol

This dissertation was a non-experimental correlational quantitative analysis of multi-clinic site locations of consecutive patients referred to or coming via direct access for physical therapy care related to chronic low back pain. It was a collection of trust surveys, TA questionnaires, and patient reported outcomes related to their low back pain and function completed by the patient participant through an interrupted time-series of prior to initial evaluation, post-initial evaluation, and at discontinuation of the current episode of care. The physical therapist participants completed a patient connection and engagement questionnaire after the second visit and at discharge along with outcomes measurement data collect at the completion of the current episode of care. Data collection was at multiple outpatient physical therapy sites with multiple physical therapists and wide patient demographics to improve generalizability of the study findings.

The research project was conducted according to the Declaration of Helsinki. All the participants were fully informed of the study content before their participation in this study and completed informed consent. Institutional Review Board (IRB) at the University of South Dakota served as the IRB of record with joint approval from Nova Southeastern University IRB.

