### **3.3.2 Instruments – Predictor variables**

Various instruments were used to measure trust during the encounter. For the purpose of this study, three of the most well studied provider-specific trust measurement scales (Trust in Physician Scale, Primary Care Assessment Survey (PCAS), and Wake Forest Scale) used in the physician and psychology literature were chosen that have items written that could easily translate to physical therapy practice and patient care. To date, none of these provider-specific trust measurement scales had been studied for use in physical therapy practice. General trust in the medical profession and physical therapy was assessed by the General Trust in Physician Scale. A TA measurement scale (Working Alliance Inventory – Short Revised) was used and was the only predictor instrument previously used in the physical therapy literature. The final instrument was developed as part of the dissertation process to assess the physical therapist's perception of their patient's connection and engagement (PT Survey of Patient Connection and Engagement) within the therapeutic process during the physical therapy encounter.

Trust in Physician Scale: The Trust in Physician Scale is one of the first instruments developed to assess a patient's interpersonal trust in their physician. The original published work

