precoded item value). Four of the seven Likert scale items (questions #1, #3, #5, #8) are reverse score items and must be recoded for final scoring (5 = precoded item value 1, 4 = precoded item value 2, 3 = precoded item value 3, 2 = precoded item value 4, 1 = precoded item value 5). For purposes of this study, the word “doctor” was replaced with “physical therapist” from the original scale. The PCAS scoring algorithms calculate a score if a respondent answers at least 50% of the items on the scale (4 items on the trust scale), the missing whole values are inputted as the respondent’s average score across all completed items for the scale. A transformed scale score can be computed as the product of the actual raw scale score minus the lowest possible raw scale score (8 on the trust scale) that is divided by the possible raw scale score range (32 on the trust scale) multiplied by 100. The Flesch reading ease score is 62.6, which equates to an 8.4 Flesch-Kincaid grade level according to Microsoft® Word 365 for Office (Redmond, WA). The scale was originally developed and tested on Massachusetts state employees on their level of trust with their primary care physician. (Appendix D)

Wake Forest Scale: The third provider specific trust measurement scale used was the Wake Forest Scale developed by Hall, et al. The Wake Forest Scale was developed to improve on the various trust measurement scales that currently had been published at that time (Anderson/Dedrick with the Thom modification, Safran, and Kao) and to be more generalized to other care providers, not just physicians. The Wake Forest Scale development was done by retaining or modifying questions from the existing scales that fit their conceptual model of trust measurement. To address areas of the trust domain that the study team did not think were fully covered, they, along with a group of experts developed additional items. After initial testing and screening of questions, it produced 26 candidate items for further testing, which ultimately produced the final 10-items that were accepted for the scale. The 10 items reflect

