### **3.3.3 Instruments – Outcome measurement variables**

The outcome measurements chosen for this study assessed the patients' progress during their physical therapy episode of care on various levels. Patient reported outcomes assessed clinical pain and functional progress by utilizing the Oswestry Disability Index 2.0 (ODI), Numeric Pain Rating Scale (NPRS), and a Global Rate of Change Scale (GROC) as these have been shown to be more responsive than physical impairment measurements.

Oswestry Disability Index 2.0: Improvement in function is a key outcome measurement for clinical conditions and the ODI has shown to have some of the best responsiveness when it comes to patients with low back pain. The ODI has been an extensively used measurement tool to evaluate function and how back pain affects an individual's ability to do daily activities. The ODI assesses function in 10 categories (pain intensity, personal care, lifting, walking, sitting, standing, sleeping, sexual activity, social life, and traveling). Version 2.0^135 was utilized for the purposes of this study. Each of the 10 categories has six statements that are scored from 0 to 5, the statement with the least disability is scored a 0 and the greatest disability scored with a 5. If more than one statement is marked, then the highest score is recorded. The overall score (index) is calculated by taking the total points added up for items answered and dividing by the total possible score (number of categories answered x 5). This number is then multiplied by 100 and rounded to a whole number. Overall index scores can be interpreted for

the range of 0-20% for minimal disability, 21-40% for moderate disability, 41-60% for severe disability, 61-80% for crippled, and 81-100% for individuals bed bound or exaggerating their symptoms. (Appendix I)

Numeric Pain Rating Scale: The NPRS is a unidimensional measurement of pain intensity in adults. It consists of an 11-point ordinal scale measuring pain from “0” = no pain to “10” = worst pain imaginable. The respondents were asked to report on current, best and worst pain in the last 24 hours. All three scores (current, best, and worst) were recorded along calculation of the average of all three being reported. This scale has been used across various diagnoses and age ranges. (Appendix J)

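### The sample size covers one correlation at 0.05, but the SAP plans at least nine trust–outcome correlations with no primary pair, multiplicity control or exploratory label

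*Combined protocol and SAP*

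**What the plan says.** Section 3.3.1 (Participant recruitment) sets 64 patients, with 20% dropout allowed for, and says this "achieves 79% power to detect a Pearson correlation of 0.400 using a two-sided hypothesis test with a significance level of 0.05". That describes a single correlation.

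The SAP states: "The primary correlational statistics was the Spearman rho". It applies that statistic to the individual trust scores, including "changes in scores over time and individual scores with the primary outcome measurements of pain, function, and global change". It later adds linear regressions of the trust scales and the outcome variables.

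Other sections supply the counts:
- Section 3.3.2 selects "three of the most well studied provider-specific trust measurement scales": Trust in Physician, PCAS and Wake Forest. It adds a general trust scale, measured once before the first visit.
- Section 3.3.3 gives one instrument each for function (ODI), pain (NPRS) and global change (GROC). The NPRS yields current, best, worst and average scores, and none is named as the pain outcome.
- Section 3.3.5 collects the three provider-specific scales before the first visit, again after it ("Upon completion of the initial visit, the patient participant completed the WAI-SR, Trust in Physician Scale, PCAS, and Wake Forest Scale"), and at the end of care. ODI and NPRS are collected at baseline and at the end.

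The SAP does not say which occasion's trust score is correlated with outcome, or whether ODI and NPRS enter as final score or as change. No visible text names a primary pair, adjusts for multiplicity or calls these analyses exploratory.

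**The concern.** The only significance level and power in the documents belong to one test, whereas the plan runs a set of tests with no order among them. Two things follow. A reader who meets a significant trust–outcome correlation cannot tell whether it was the one the study was sized for. And if each is judged at 0.05, the chance that at least one of them is significant by accident is several times 5%. Whether trust relates to outcome in physical therapy rests largely on these correlations, so the status of each one determines how much the findings can bear.

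**Working it through.** **Inputs.** From section 3.3.1: 64 enrolled, 20% dropout, correlation 0.400, two-sided 0.05, 79% power from 1000 simulated bivariate normal samples. From sections 3.3.2, 3.3.3 and 3.3.5: 3 provider-specific scales, 3 outcomes, 3 occasions. Assumed, because the documents give no values: correlations of 0.3–0.9 among scales and 0.3–0.7 among outcomes.

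**Step 1: the plan's own figure.** Evaluable patients: 64 × 0.8 = 51.2, so 51.
- Pearson test, Fisher z: Φ(atanh(0.4) × √(51 − 3) − 1.960) = Φ(0.4236 × 6.928 − 1.960) = Φ(0.975) = 83.5%. Simulation gives 84.1%.
- Spearman test on bivariate normal data with correlation 0.4: simulation gives 79.4% (40,000 samples) and 79.6% (100,000 samples).
- All 64 analysed: Pearson 91.1%, Spearman 88.3%.

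The standard error of a 79% estimate from 1000 samples is √(0.79 × 0.21 / 1000) = 1.3 points. A Pearson test on 51 patients is about 5.1 / 1.3 ≈ 4 standard errors away, while a Spearman test on 51 is within one. The stated 79% therefore reproduces for one Spearman test on 51 patients, although the text mentions only a Pearson correlation and gives neither the test nor the number 51.

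**Step 2: the number of tests.**
- One occasion: 3 scales × 3 outcomes = 9.
- Three occasions: 9 × 3 = 27.
- Before the first visit, if the general trust scale counts: 4 × 3 = 12.
- Change scores and alternative NPRS scores add more.

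Nine is the minimum.

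**Step 3: false positives in 9 tests at 0.05, with no true association.**
- Expected number: 9 × 0.05 = 0.45, whatever the correlations.
- Independent tests, as a ceiling: 1 − 0.95⁹ = 37.0%. This is too high here, because the scales overlap and so do the outcomes.
- Simulated Spearman tests, n = 51, 20,000 replicates in each of 15 combinations of the assumed correlations: 18.8% to 34.8%. With scales correlated at 0.9: 18.8% to 23.3%.

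Section 3.3.2 says the Wake Forest Scale was built by "retaining or modifying questions from the existing scales", which suggests high correlation among scales. It also says new items were written and gives no count of shared items, so it does not narrow the range.

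**Step 4: what formal control over all 9 would cost.** Holm's strictest step is 0.05 / 9 = 0.00556. At that level a single Spearman test on 51 patients has about 50% power for a correlation of 0.40 (simulated 49.8% and 50.1%), against about 79% at 0.05. Holm held the family-wise error at 2.9% to 5.2% in the same 15 combinations.

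**The case against.** The best defence is that this is a "non-experimental correlational quantitative analysis", done as a dissertation. The SAP itself sets no significance level, success criterion or decision rule; 0.05 appears only in the sizing statement. Comparing instruments is part of the purpose, since none of the three provider-specific scales had been studied in physical therapy and the SAP also correlates them with the working alliance inventory. On this view family-wise control is not required, and one sentence is missing. Much of that stands, and it is why an exploratory label is the main remedy here rather than a correction. It does not remove the point: a correlational design is not the same as a stated exploratory status, and a powered two-sided test beside outcomes called primary invites a confirmatory reading.

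Four stronger readings are tempting and are not supported:
- A reader might infer that the SAP declares all nine correlations primary. The word attached to Spearman's rho can simply mean the main method; only the three outcomes are clearly called primary.
- A reader might infer that the 79% is wrong. It reproduces for a Spearman test on 51 patients, but that this was the calculation is an inference for the sponsor to confirm.
- A reader might infer that one favourable result will be selected. Nothing in the text says so; it only leaves the choice open.
- A reader might infer that the plan must now pick one pair. The documents give no basis for preferring a scale, and the SAP is written in the past tense, so a pair chosen now might not be prespecified.

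The visible numbering begins at section 3.3. Aims or hypotheses may have been stated elsewhere, so the absence is established only for the text available.

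**Conclusion.** The point holds in a limited form. The power statement covers one correlation; the SAP plans at least nine between trust scales and outcomes, and the visible text gives no hierarchy, multiplicity control or exploratory status. Judged each at 0.05, nine tests carry roughly four to seven times the nominal error (19 / 5 = 3.8; 35 / 5 = 7).

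That size depends on three things: testing each at 0.05, which the SAP does not itself state; 51 evaluable patients with no true association in any pair; and assumed correlations among scales and among outcomes. If trust truly relates to outcome, the false-positive rate is a smaller worry, but it remains unclear which result the 79% covers. The weakness affects what may be concluded from the correlations and regressions, and does not make the enrolment target inadequate for a single test.

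**What to change.** **In the SAP.** Label all trust–outcome correlations, and the linear regressions of the same scales and outcomes, as exploratory. Report every one with a 95% confidence interval, state how many were run, and make no confirmatory significance claim from any single result.

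**Only if a pair was fixed before results were seen**, name it as the single primary test at two-sided 0.05. State the scale, the occasion and the outcome; which NPRS score is used if pain is the outcome; and whether ODI or NPRS enters as the discharge score or as change. A pair chosen later must be disclosed as post hoc.

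**If the sponsor wants all nine as confirmatory**, apply Holm and state that power for a correlation of 0.40 is about 50% at the strictest step.

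**In section 3.3.1.** The sponsor should confirm which test and how many evaluable patients the 79% describes, and say that it covers one correlation only.

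**Cost.** Wording in two places, confidence intervals that the SAP does not now plan, and weaker claims from individual results. No further patients or data are needed, and the target of 64 stays.

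### The only planned test of change in trust, Friedman's, uses patients with all three time points and gives one overall p-value per scale, so at the planned 20% dropout it can discard usable first-visit scores and, without planned contrasts, does not locate the change.

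*Combined protocol and SAP*

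**What the plan says.** The SAP states that Friedman's "analysis of variance looked at changes in individual trust measurement scores over time from pre-initial visit, post-initial visit, and discharge". It names no other test of change over time. It plans no pairwise comparison, no multiplicity rule for such comparisons and no estimate of the size of change. Its stated reason for rank methods is that the outcomes are ordinal.

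Section 3.3.5 collects the three provider-specific trust scales (Trust in Physician, PCAS, Wake Forest) before the initial visit and at two later times:
- After the first visit: "Upon completion of the initial visit, the patient participant completed the WAI-SR, Trust in Physician Scale, PCAS, and Wake Forest Scale".
- At the end of care: "Upon discontinuation of the current episode of care or the end of 6 months of care".

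Section 3.3.1 says that the sample "was set for a total of 64 patient participants", "with an included 20% dropout rate". The missing-data rules in sections 3.3.2 and 3.3.3 cover unanswered items within a PCAS, General Trust or ODI form. None covers a form missing at a whole time point.

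**The concern.** Friedman's test ranks the three scores within each patient, so a patient without a discharge form contributes nothing. That includes the change across the first visit, for which the data may be complete. The discharge form comes at the end of the episode or at six months, so it is the one most exposed to loss.

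Two things are at stake. The first is precision, and possibly bias: if patients who leave early trust their therapist less, the completers are a selected group. The second is interpretation. The design brackets the first visit with a form on each side and adds a third at the end of care, but one overall p-value does not say whether trust moved at the first encounter or over the course of treatment.

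**Working it through.** **1. Completers implied by the plan.** Inputs from section 3.3.1: N = 64, 20% dropout, a design that "achieves 79% power to detect a Pearson correlation of 0.400", and a "two-sided hypothesis test with a significance level of 0.05". 64 × 0.8 = 51.2, so about 51 completers and 13 dropouts. Simulating a bivariate normal correlation of 0.40 at n = 51 gives 79.7% power for a Spearman test, which matches the stated 79%. A Pearson test at n = 51 would give 84.2%. The plan's figure is therefore consistent with 51 analysed patients.

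**2. Scores discarded per scale.** The documents do not say when dropouts leave, so the pattern is assumed.
- All 13 miss only discharge: collected 3 × 64 − 13 = 179; used 3 × 51 = 153; discarded 26 (26/179 = 14.5%).
- All 13 give only the pre-visit form: collected 3 × 64 − 26 = 166; used 153; discarded 13 (7.8%).
- Missing only discharge, at 10% dropout: 12 of 186 (6.5%). At 30%: 38 of 173 (22%).

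**3. Precision of the first-visit change.** The standard error is proportional to 1/√n, so √(64/51) = 1.12, or 12% larger with 51 patients. This is the upper end at 20% dropout. If dropouts gave only the pre-visit form, they have no pre-to-post pair and nothing is lost for this contrast.

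**4. Bias if dropout depends on trust.** Assumptions, none of them from the documents: standard normal scores; correlations 0.6 (pre, post), 0.7 (post, discharge) and 0.5 (pre, discharge); 20% logistic dropout on the post-visit score y, with p(y) = 1/(1 + exp(−(a − s·y))); no true change. Completers' mean post-visit score is m = E[y(1 − p(y))]/0.8. Their apparent changes are (1 − 0.6)m from pre to post and (0.7 − 1)m from post to discharge.
- s = 1: m = 0.173, giving +0.069 and −0.052 SD.
- s = 1.5: m = 0.227, giving +0.091 and −0.068 SD.

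**5. Type I error in that scenario** (nominal 5%, repeated simulations of 4,000 to 6,000 studies):
- Friedman on completers: 5.0 to 5.8% at s = 0; 6.3 to 7.1% at s = 1; 7.9 to 8.8% at s = 1.5.
- Pre-to-post signed-rank test on all 64: 4.6 to 5.1% throughout. On completers only, at s = 1, it rises to between 8% and 9%, so the excess comes from restricting to completers.
- Post-to-discharge signed-rank test, which can use completers only: about 7 to 8% at s = 1 and about 9% at s = 1.5.
- Skillings-Mack on all available scores: about 5.3%.

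**The case against.** The strongest case against is that this is a supporting analysis. The SAP makes Spearman's rho the primary correlational statistic, section 3.3.1 sizes the study for a correlation, and 51 completers is the number that calculation allows for. This stands. A reader might infer that the trial's main result or its power is compromised, but nothing here touches either.

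A reader might also infer that Friedman's test cannot show when trust changed. That is too strong: pairwise tests with multiplicity control can be added to it. The gap is that none is specified.

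The loss is conditional. It would be wrong to state as fact that 13 patients have both early forms, because the post-visit form sits behind a second online link and can be missed too. Some losses also come from the protocol's own exclusions (medical referral, and the 80% same-therapist rule), and the documents do not say whether the 20% covers them. The gift card for completing all three sets of forms may reduce missingness. No passage links dropout to low trust.

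Setting Friedman's roughly 7% error on completers against 5% for a two-time-point test on 64 patients is not like for like, since the hypotheses differ. The fair comparison is Friedman with and without dependent dropout, and that difference is modest. Finally, replacing Friedman by signed-rank tests throughout would not cure the bias, because the post-to-discharge test rests on the same completers.

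What remains is that the plan expects dropout, has no rule for a missing time point, and names no contrast.

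**Conclusion.** The point holds as a should-fix matter for the trust-over-time analysis. The missing contrasts and the missing rule for an absent time point follow directly from the text. The size of the loss depends on when dropouts leave. At 20% dropout it ranges from 13 of 166 to 26 of 179 scores per scale, and the inflation of the first-visit standard error ranges from none to 12%. The bias, 0.05 to 0.09 SD with a type I error of 6 to 9%, is modest. It depends wholly on assumed correlations and an assumed dependence of dropout on post-visit trust of 1 to 1.5 log-odds per SD.

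**What to change.** Among patients who remain eligible under the protocol's exclusions, pre-specify for each of the three trust scales:
1. A Wilcoxon signed-rank contrast from pre- to post-initial visit, on all patients with both forms.
2. An overall test using all available scores: Skillings-Mack, which keeps the SAP's rank-based rationale, or a mixed model with time as a factor. Keep Friedman on completers as a sensitivity analysis.
3. A post-initial-visit to discharge estimate from the mixed model, which is valid if dropout depends only on observed scores. If a signed-rank test is also reported, label it completer-only, because it does not remove dropout bias.
4. Holm adjustment across the two contrasts, and the number of patients contributing at each time.

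The cost is some SAP wording and a little more analysis work, with no new data. The mixed model treats summed scores as continuous, which the SAP's linear regression already does.
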